### **3.0 Research Methods and Study Design**

To accomplish our aims we propose a cluster randomized controlled trial (cRCT) in the Eastern District of Ghana. The study is designed in collaboration with the Dodowa Health Research Center under the direction of [name] (Co-PI). Health facilities were selected based the number of deliveries and average gestational age of women in each facility and matched so that each pair of facilities are similar to each other with regard to these matching factors. For each pair of facilities, one will randomly be assigned to group ANC (intervention) and the other to routine, individual ANC (control). The locations of the chosen facilities ensure that participating facilities will be far enough apart to minimize the likelihood of cross-group contamination. The unit of randomization is the health facility stratified by site and gestational age. Cluster randomization will be produced through nbpMatching package from R software. During the study, 1680 participants will be randomized into 120 groups of 12 to 14 women of the same gestational age at the cluster site. This will result in approximately 8-10 groups per site during the study period.

### **3.1 Recruitment and Informed Consent**

Recruitment of women will occur at individual health facilities. The research staff will work with clinic staff to identify women who meet the eligibility criteria and are healthy enough to discuss enrolling in an ANC intervention. The RA will inform health facility staff when they will be at the clinic and available to women interested in learning more about the study. Midwives will identify women who are: 1) less than 20 weeks gestation; 2) speak Dangme, Ga, Aka, Ewe, or English; 3) over the age of 15; and 4) are not considered high risk. Thus, the midwife (as a medical professional) will make the assessment that a woman is healthy enough to participate in the study.

The midwife will instruct women who qualify to should talk to the RA if they are interested in learning more about the study. Women who approach the RA will be read an approved

recruitment script. Those who are willing to participate will be taken through an informed consent procedure and will then complete baseline data collection.

Due to the high rates of illiteracy in Ghana, we will ask for a waiver of the standard written informed consent procedure. Instead, oral consent will be obtained individually from all participants and witnessed. The procedures for informed consent will include: 1) We will prepare an informed consent document in English that will be translated into Dangme, Ga, Akan, and Ewe; 2) The informed consent document will be read aloud individually to all potential participants in private; 3) The Ghanaian RA will ask the potential participant questions to ensure understanding of the research process and informed consent document and will invite questions until the information is clear; and 4) as we anticipate that many participants will not be able to read the form themselves, a witness (health facility staff) will sign that he/she was present while the benefits, risks, and procedures were read to the participant, that all questions were answered, and that women voluntarily agreed to take part in the research. A teach-back method will be used to confirm participant comprehension of the study requirements and methodology. The RA will ask potential participants to describe their understanding of the study's purpose, procedure, risks, and benefits using open-ended prompts and repeating the material until understanding is achieved.

The participant will sign, or mark with a thumbprint, the informed consent and the RA will use the camera on the encrypted tablet to take a shot of the signed/ thumbprint page. The image will be stored similar to all study data; that is, when internet connection is not available, data will be collected off-line and stored in a password protected file on the encrypted tablet. Once a connection is available, these data will be uploaded, managed, and stored on a secure server.

Participants will be given their signed/thumbprint informed consent that contains the following elements: title of project, name, credentials and institution of researcher, invitation to participate, statement that the study involves research, description of the research, description and length of participant involvement, benefits and risks, compensation, confidentiality, voluntary participation, and contact information.

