### Primary Outcomes

- Attendance at 4+ ANC visits
- Facility birth
- Four postnatal/postpartum check-ups for both mother and newborn in the first 6 weeks after birth

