### **3.2 Inclusion/Exclusion Criteria**

Inclusion criteria are as follows: 1) willingness to participate in the study; 2) less than 20 weeks' gestation 3) able to speak Dangme, Ga, Akan, Ewe, or English; 4) over the age of 15 years; and 5) no history of medical problems that would indicate the participant might be considered "high risk" (e.g., hypertension, insulin-dependent diabetes mellitus) and thus requiring a more individualized approach to care.

In the eastern region, 10.4% of females age 15-49 have never attended school and only 15.7% percent have completed secondary school or higher. Thus, we will not limit participation based on literacy, however we will control for years of education and literacy status in the analysis. This is a study of an intervention for pregnant women to improve maternal and newborn outcomes; thus no males will be included.

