## Measures

Time Point	Domain	Data collection
T0 – Baseline	Demographic Characteristics (Age, gravida, living children, marital status, age at marriage, pregnancy history, medical history)	Face-to-face Survey
	Self-efficacy	
	Recognize problems and understands health information	Face-to-face Survey
	Care-seeking history	Face-to-face Survey
	Educational Background	
	Level of Education	Face-to-face Survey
	Prior Knowledge	
	Ability to identify danger signs/BPCR	Face-to-face Survey
	Health Literacy Skills (understanding, engagement with health system)	Face-to-face Survey
	Ecological Influences (social support, community and family resources)	Face-to-face Survey
T1 – Third trimester	Comprehension of Stimuli (identification of danger signs, BPCR)	Face-to-face Survey
	Self-determination	
	Intent to use family planning / preparation for birth	Face-to-face Survey
	Two or more tetanus toxoid vaccines / Completion of ITP 2 malaria prophylaxis	ANC Card
T2 – Post birth	Clinical Health Related Outcomes (Place of birth, hemoglobin levels, newborn birth weight, maternal & newborn morbidities, stillbirth, postpartum visit within 2 days post birth)	ANC Card
	Self-determination	
	Attendance at 4 or more ANC visits	ANC Card
	Adherence to care - Number of ANC Visits	ANC Card
	Health Related Behavior (Maternal and newborn postpartum visits)	Survey
	Clinical Health Related Outcomes (Perinatal mortality (<7 days), maternal morbidities)	ANC Card
T3 – Six months postpartum	Health Related Behavior (Uptake of modern family planning, exclusive breastfeeding, 4 postnatal check-ups completed on both mother and newborn in first 6 weeks)	Survey via phone
	Clinical Health Related Outcomes (Neonatal mortality(<28 days), maternal morbidities)	Survey via phone
T4 – One year postpartum	Health Related Behavior (Repeat pregnancy)	Survey via phone
	Clinical Health Related Outcomes (Infant immunized per EPI schedule; maternal morbidities)	Self-report Survey via phone

During all visits midwives will record Clinical Health Related Outcomes (Place of birth, hemoglobin levels, newborn birth weight, maternal & newborn morbidities, stillbirth, postpartum visit within 2 days post birth) on the women's ANC card. These data will be collected by the RA during all study visits except baseline.

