### **3.5 Intervention - Description of the Model for Group Antenatal Care**

The group ANC model was modified from a curriculum initially developed by the American College of Nurse Midwives to mobilize communities in low-resource countries for early problem identification of pregnancy related problems and referral. Using an iterative process with Ghanaian providers, pregnant women, and stakeholders as well as content experts from the U.S. to ensure local and cultural relevance and the WHO Standards for Maternal and Neonatal Care, the group ANC model was developed and tested for acceptability and feasibility by [name] and her Ghanaian team for the first time in a clinical setting in Ghana. At the core of the model is a negotiation process that acknowledges some health messaging may be in conflict with cultural beliefs. The model allows participants to incorporate safe, feasible, and culturally acceptable health beliefs into self-care actions by being inclusive of traditional practices that are not

harmful. Participants and the facilitator ‘agree’ on safe and acceptable actions within the context of the setting that are then practiced by the group.

The intervention consists of nine meetings; one individual meeting and eight group meetings. At the initial ANC visit, women are assigned to a small groups with 12-14 women of similar gestational age. Women meet individually with the midwife and the standard complete history and physical exam as well as lab tests are completed; group visits start at the second ANC visit. Prior to the start of each group, blood pressure, weight, and a urinalysis are measured for each woman. The midwife, health facility staff member, and patients then sit in circle facing one another for a 60-90 minute facilitated discussion. The health facility staff member will assist the midwife with group activities. The model uses strategies such as story-telling, peer support, and demonstration and teach-back to enhance its effectiveness. Health literacy is incorporated as an integral part of clinical practice within the model – not as an add-on to care.

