### **3.6 Control - Antenatal Care as Usual.**

The control arm is standard antenatal care delivered at health facilities in Ghana. During these visits women meet individually with a midwife who conducts a brief history and physical exam including weight and blood pressure. Following the standard ANC visit, women enrolled in the study at a control site will complete the same survey as the women in the intervention arm. Follow-up visits are the same across conditions.

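### The entry visit is not fixed, and antenatal visits made before enrolment count towards an Aim 2 primary outcome without being recorded at baseline or adjusted for

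*Combined protocol and SAP*

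**What the plan says.** **Entry, both arms.** Section 3.1 gives the timing rule as "Midwives will identify women who are: 1) less than 20 weeks gestation". Section 3.2 repeats it ("willingness to participate in the study; 2) less than 20 weeks' gestation"). None of the criteria in either section concerns the visit number or earlier antenatal care in this pregnancy. Recruitment follows the research assistant's presence at the clinic: "The RA will inform health facility staff when they will be at the clinic and available to women interested".

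**Intervention arm.** Section 3.5: "At the initial ANC visit, women are assigned to a small groups with 12-14 women of similar gestational age", and "group visits start at the second ANC visit".

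**Control arm.** Section 3.6: "Following the standard ANC visit, women enrolled in the study at a control site will complete the same survey". It does not say which visit this is.

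**Outcome.** The first Aim 2 primary outcome in Section 2.0 is "Attendance at 4+ ANC visits". The Measures table in Section 3.3 lists it at T2, together with "Adherence to care - Number of ANC Visits", both read from the ANC card. No starting point for the count is given. Section 4.0 models the number of attendances with an identity link and reports the average difference.

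**Adjustment.** The covariates in Section 4.0 include study site, gestational age and demographic and history variables, but not visits made before enrolment. Baseline measurements are named as covariates for Aim 1 only. Under Section 3.3, medical information at T0 is self-reported, and the research assistant takes card data at every study visit except baseline.

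**The concern.** A woman who enters at her second or third visit has already shown that she returns for care. Her earlier visits count towards the outcome, and group care could not have influenced them.

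This matters for the comparison only if the entry visit differs between arms, and the design leaves room for that. Section 3.7 reports the site allocation as already done, while Section 3.1 describes recruitment as still to come, with midwives at those sites picking out eligible women. Intervention sites must fill groups that Section 3.5 forms at initial visits; control sites have no such constraint. Randomising sites does not protect against selection of women after allocation.

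If later entry were more common in controls, a real gain in attendance would be partly hidden. If it were equally common in both arms, the estimate would be unbiased but would carry variation that the intervention could not change. As planned, the data might not show which of these had happened.

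**Working it through.** **The plan's own figures.** There is no effect size, standard deviation, intracluster correlation or power for attendance to reproduce. The sample size reproduces (120 groups × 14 women = 1680) but does not bear on this point. The only attendance rate in the documents is the national 87.3% with four or more visits (Section 1.1), used here as the base rate.

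**Formula.** Let p1 and p2 be the probabilities of reaching four visits for women who enter at visit 1 and visit 2. Let fC and fI be the shares of control and intervention women who enter at visit 2. With no true effect,

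artefact = (fC − fI) × (p2 − p1).

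The documents give neither share. I assume fC = 20–50% and fI = 0, which is a deliberately one-sided case.

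**Model A: constant probability r of returning after each visit.**
- p1 = r³ = 0.873, so r = 0.9557
- p2 = r² = 0.9134, so p2 − p1 = 0.0404
- fC = 20%: 0.20 × 4.04 = 0.8 points
- fC = 50%: 0.50 × 4.04 = 2.0 points
- Spurious odds ratio (intervention to control) at 50%: (0.873/0.127) ÷ (0.8932/0.1068) = 0.82

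**Model B: visits after the entry visit are Poisson with mean 5** (chosen because p1 is then close to 87.3%).
- p1 = P(X ≥ 3) = 0.875; p2 = P(X ≥ 2) = 0.960
- p2 − p1 = P(X = 2) = e⁻⁵ × 5²/2 = 0.0842
- fC = 20%: 1.7 points; fC = 50%: 4.2 points

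Model B is the less favourable of the two, because it gives a later entrant as many remaining visits as a first-visit entrant although less of her pregnancy is left.

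**Range.** The two models together give 0.8–4.2 points, roughly 1–4. The most that attendance can rise above 87.3% is 100 − 87.3 = 12.7 points, so this is 0.8/12.7 = 6% to 4.2/12.7 = 33% of the available room.

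**Sensitivity (Model A).**

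| Base rate | fC | fI | Artefact (points) |
|---|---|---|---|
| 70% | 50% | 0 | 4.4 |
| 80% | 50% | 0 | 3.1 |
| 87.3% | 50% | 0 | 2.0 |
| 95% | 50% | 0 | 0.8 |
| 87.3% | 25% | 10% | 0.6 |
| 87.3% | 25% | 25% | 0 |

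**Number of visits (Model A, capped at the nine meetings of Section 3.5).** Mean = s + Σ rᵏ for k = 1 to 9 − s, where s is the entry visit. This gives 7.56 for s = 1 and 7.86 for s = 2, a difference of 0.30. With fC = 20–50%, the control mean rises by 0.06–0.15 visits.

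**The case against.** The strongest reply is that the plan has one entry rule and one recruitment procedure for both arms. A reader might infer from Sections 3.5 and 3.6 that intervention women enter at their first visit while later entry happens mainly in controls. The documents do not say so. Section 3.5 describes when groups are formed; it is not an eligibility limit, and it does not bar a woman from consenting later. Silence in Section 3.6 is not permission for late entry in controls alone. This part of the reply stands: differential entry is possible, not stated.

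Second, a whole-pregnancy total is the natural reading of a 4+ outcome and matches the benchmark in Section 1.1. It does not depend on the date of consent: a woman who makes five visits scores five whether she enrols at her first or her second. That also stands. It would be wrong to say that each earlier visit simply inflates the outcome by one; the mechanism is selection of women who have already returned.

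Third, gestational age is already a covariate, and care-seeking history is surveyed at T0. This stands only in part. Women at the same gestation can have made different numbers of visits, and the plan does not say whether that history covers the current pregnancy.

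Finally, one might fear a head start in knowledge for later entrants. That is not pursued, since Aim 1 already adjusts for baseline.

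**Conclusion.** The gap is real but conditional. The entry visit is unfixed, the pre-enrolment visit count is not specified for recording at T0, and the attendance analysis does not adjust for it. Bias against the intervention follows only if more controls than intervention women enter after a return visit.

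The figure of about 1–4 points rests on three assumptions: the 20–50% against 0% split, entry no later than visit 2, and a base rate near 87.3%. A larger figure is easy to produce. Poisson later visits with mean 4 give 0.762 against 0.908, and so 2.9–7.3 points for the same split. That needs a 4+ rate of about 76% among first-visit entrants, which nothing in the documents supports. The point is worth acting on because the protection is almost free and, with women selected after allocation, randomisation alone does not supply it.

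**What to change.** 1. Reconcile Sections 3.1 and 3.2 with Sections 3.5 and 3.6 so that the entry visit is stated and is the same in both arms. Restricting entry to the first visit is one way, but it would exclude women already past that visit and is not essential if the steps below are taken.
2. Have the research assistant record from the ANC card the number of visits in this pregnancy dated before T0. This assumes that the card shows visit dates. It can be done at T0, or at T1 when the card is read anyway.
3. Keep the whole-pregnancy total as the outcome. An unadjusted count from T0 would penalise later entrants, who have less pregnancy left, and could reverse the bias.
4. Add the pre-T0 count, with gestational age at enrolment, as a covariate in the model for number of visits, and in the 4+ model if one is fitted (Section 4.0 describes only the former). With the identity link nothing is lost by keeping the total: subtracting a covariate from the outcome lowers that covariate's coefficient by one and leaves the arm coefficient unchanged.
5. Report the pre-T0 count by arm, so that readers can see whether entry differed.

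The cost is one extra card field and one covariate.

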### 3.7 Randomization

There are 14 sites in the study. We randomized these 14 sites into the control group and the intervention group. To improve the balance between the two groups and improve the efficiency of estimating intervention effect, we used the facility type, district of site, and ANC registrant numbers in 2018 to conduct matched randomization. The randomization process were carried out using nbpMatching package from R software.

Control Sites				Intervention Sites			
Facility	Facility Type	District	ANC 2018	Facility	Facility Type	District	ANC 2018
Adawso	Health Center	Akuapim North	403	Akuse	Hospital	Lower Manya Krobo	378
Abiriw	Clinic	Akuapim North	322	Adkukrom	Health Center	Akuapim North	299
Tetteh Quarshie	Hospital	Akuapim North	654	Atua	Hospital	Lower Manya Krobo	715
St Martin's	Hospital	Lower Manya Krobo	1081	Nsawam	Hospital	Nsawam	4930
Nsawam	Health Center	Nsawam	901	Adoagyiri	Health Center	Nsawam	817
Djankrom	Health Center	Nsawam	295	Klo Agogo	Polyclinic	Yilo Krobo	237
Nkurakan	Health Center	Yilo Krobo	469	Somanya	Polyclinic	Yilo Krobo	616

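### Women are screened after their facility is allocated, by midwives who can be inferred to know the arm and who apply an open high-risk criterion, so the arms can enrol women of different risk

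*Combined protocol and SAP*

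**What the plan says.** **Order of events.** Section 3.7 reports allocation as done, "We randomized these 14 sites into the control group and the intervention group", and lists seven facilities per arm by name. Section 3.4 also refers to seven facilities already in the intervention arm. Section 3.1 puts enrolment in the future: "Recruitment of women will occur at individual health facilities". Section 3.0 uses the future tense for the assignment, but no section has women identified or enrolled before it. Section 3.0 also sets the level of allocation: "The unit of randomization is the health facility stratified by site and gestational age".

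**Who screens.** Section 3.1: "Midwives will identify women who are: 1) less than 20 weeks gestation", followed by language, age and not being considered high risk. It then says: "Thus, the midwife (as a medical professional) will make the assessment that a woman is healthy enough to participate in the study". The same section says that research staff will work with clinic staff to find eligible women.

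**The criterion.** Section 3.2 requires no history of medical problems that might place a woman in the high-risk category. It gives hypertension and insulin-dependent diabetes as examples and adds the reason "and thus requiring a more individualized approach to care".

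**Second step.** Women who qualify decide whether to speak to the research assistant (RA): "Women who approach the RA will be read an approved" recruitment script.

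**Care in each arm.** Section 3.5, on group sessions: "The midwife, health facility staff member, and patients then sit in circle facing one another for a 60-90 minute facilitated discussion". Section 3.6 describes control care as individual visits with a midwife.

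**The concern.** In a cluster trial, randomising facilities balances the populations that attend them. It does not balance the women enrolled if enrolment comes later and depends on someone who knows the allocation.

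Three features come together here. Allocation comes first. The person judging risk works at a facility with one arm. The judgement is open-ended, and its stated reason relates to how care is delivered. A control-site midwife has little cause to exclude a borderline woman on that ground, because her care is individual anyway. An intervention-site midwife has the protocol's own reason to do so. What a woman expects of care at her facility may also affect whether she approaches the RA.

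The outcomes most exposed are the Aim 3 primary outcomes, maternal morbidity and birth outcome, which depend on underlying risk and have no baseline equivalent to adjust for. The plan describes no concealment at screening, no eligibility check by someone unaware of the arm, and no log of women screened, excluded or declining. Differential screening would therefore leave little trace.

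**Working it through.** **The plan's own figure.** 120 groups × 14 women = 1680, as stated in section 3.0 (at the top of its 12 to 14 range). 1680 / 14 facilities = 120 women per facility, or 840 per arm. The plan gives no event rate, intracluster correlation (ICC) or expected exclusion rate, so the size of any bias cannot be derived from it. What follows is an illustration.

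**Which links are stated and which are inferred.**
- Allocation before recruitment: stated (3.4, 3.7, 3.1).
- Midwife judges health and risk: stated (3.1).
- Midwife knows the arm: inferred. Allocation is by facility and already made, and midwives take part in the group sessions (3.5).
- Criterion applied more strictly at intervention sites: possible from the wording of 3.2, not stated.

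**Assumptions.** No true effect. Outcome risk p0 = 0.10 in ordinary women. A share q of attenders (5% to 20%) is borderline, with k = 2 to 3 times that risk. Intervention sites exclude an extra fraction e (25% to 100%) of them, control sites none. ICC 0.01 to 0.05. Seven equal clusters of 120 per arm. No covariate adjustment.

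**Formulas.**
- Control risk: pC = p0 × [1 + q(k − 1)]
- Borderline share left at intervention sites: qI = q(1 − e) / (1 − qe)
- Intervention risk: pI = p0 × [1 + qI(k − 1)]
- Odds ratio: [pI/(1 − pI)] / [pC/(1 − pC)]
- Design effect: 1 + 119 × ICC = 2.19 at ICC 0.01 and 6.95 at ICC 0.05
- Standard error: √{design effect × [pC(1 − pC) + pI(1 − pI)] / 840}
- Rejection rate: two-sided 5% t test on 12 degrees of freedom, noncentral t. This stands in for the planned mixed model.

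**Middle case** (q = 0.10, e = 0.5, k = 3).
- pC = 0.10 × (1 + 0.10 × 2) = 0.120
- qI = 0.05 / 0.95 = 0.0526
- pI = 0.10 × (1 + 0.0526 × 2) = 0.1105
- Odds ratio = 0.1243 / 0.1364 = 0.91
- Standard error at ICC 0.01 = √(2.19 × 0.2039 / 840) = 0.0231, against a difference of 0.0095; rejection rate 0.067
- At ICC 0.05, rejection rate 0.055

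| q | e | k | pC | pI | Odds ratio | Rejection, ICC 0.01 | Rejection, ICC 0.05 |
|---|---|---|---|---|---|---|---|
| 0.05 | 0.25 | 2 | 0.1050 | 0.1038 | 0.99 | 0.050 | 0.050 |
| 0.10 | 0.50 | 3 | 0.1200 | 0.1105 | 0.91 | 0.067 | 0.055 |
| 0.10 | 1.00 | 3 | 0.1200 | 0.1000 | 0.82 | 0.129 | 0.074 |
| 0.20 | 1.00 | 3 | 0.1400 | 0.1000 | 0.68 | 0.349 | 0.143 |

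The direction is assumed. If control sites did the extra excluding, the odds ratios would invert; the middle case would become 1/0.91 = 1.10. Enrolling more women would not remove the bias.

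**What the planned analysis does.** Intention-to-treat (4.0) keeps enrolled women in their arm and says nothing about women never enrolled. Medical and pregnancy history enter the models (4.0), with precision as the stated aim. If screening acted only on recorded history and the model were right, comparing women with the same history would remove the bias. However, medical information at baseline is self-reported after consent (3.3), and selection on factors nobody records is untouched. Adjustment for baseline scores is stated for Aim 1 only.

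**The case against.** The written criteria are the same in both arms and rest on medical history. Section 3.1 speaks of being healthy enough for the study, not for group care, and involves research staff in identification. One approved script is described, with no version per arm. Section 4.0 promises CONSORT-guided reporting and full disclosure of baseline characteristics. Borderline women enrolled at control sites would show up in recorded history, which the models include. All of this stands, and it narrows the point.

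A reader might infer more than the documents support:

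- **That midwives select by suitability for group care.** Section 3.2 tests history; the need for individual care is only the reason given for it.
- **That the midwife who screens is the one who leads the groups.** Section 3.4 gives 2 to 4 midwives per intervention facility and does not say this. Knowledge of the arm is a fair inference, not a stated fact.
- **That adjustment is useless because high-risk women have been excluded.** If one arm excludes more strictly, history varies in the other, and adjustment does part of the work.
- **That the trial will show a false benefit.** No section establishes that screening will differ, or which way.

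What remains is an open criterion, applied after allocation by staff at the allocated site, with no planned record of whom they turn away.

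**Conclusion.** The concern holds as a gap in the design: the arms can enrol women of different risk, and the plan could neither prevent nor detect this well. It matters most for Aim 3. Aim 1 has some protection from baseline adjustment, and no bias has been shown for the behavioural outcomes of Aim 2.

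The size is unknown. On the assumptions listed, mild differential screening is negligible (odds ratio 0.99), a middle case is modest (0.91, rejection 0.055 to 0.067), and only near-complete one-sided exclusion of a sizeable, high-risk group is serious (0.68, rejection up to 0.35 at ICC 0.01). Ratios near 0.8 belong to complete one-sided exclusion and should not be read as a central estimate. Adjustment for recorded history would shrink these figures by an amount that the documents do not allow one to state. The change is worth making because it is cheap, not because bias has been shown.

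**What to change.** 1. Replace the open judgement in sections 3.1 and 3.2 with a closed yes/no list of high-risk history items. The investigators choose the items. The list is identical in both arms and is completed before group care is discussed with the woman.
2. Remove the phrase about individualized care from the criterion.
3. State that the same approved script is used at all 14 sites.
4. On the days when the RA attends, log for each facility and arm the women under 20 weeks who were screened, excluded (by reason), not referred, and declined. Report these counts in the CONSORT flow.

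The log is limited to RA days because RAs attend at announced times, and the 14 sites had 12,117 ANC registrants in 2018 (4,125 control + 7,992 intervention, summed from section 3.7) against 1680 participants. Sending every woman to the RA would not clearly be cheap.

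The cost is a protocol edit, a short form and log for existing staff, and slightly less clinical discretion at screening. An unblinded midwife still completes the form, so the bias is reduced and made visible, not removed.
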